8.1.2 LGG RANO

Complete Response – CR (requires *all* of the following):

a) Complete disappearance of the lesion on T2 or FLAIR imaging (if enhancement had been present, it must have resolved completely);

b) no new lesions, no new T2 or FLAIR abnormalities apart from those consistent with radiation effects, and no new or increased enhancement;

c) patients must be off corticosteroids or only on physiological replacement doses;d) patients should be stable or improved clinically

Partial Response – PR (requires *all* of the following compared with the baseline scan):

a) greater than or equal to 50% decrease in the product of perpendicular diameters of the lesion on T2 or FLAIR imaging sustained for at least 4 weeks compared with baseline;

b) no new lesions, no new T2 or FLAIR abnormalities apart from those consistent with radiation effects, and no new or increased enhancement;

c) patients should be on a corticosteroid dose that should not be greater than the dose at time of baseline scan, and should be stable or improved clinically

PI: [name]

Minor Response – MR (requires *all* of the following):

a) a decrease of the area of non-enhancing lesion on T2 or FLAIR MR imaging between 25% and 50% compared with baseline;

b) no new lesions, no new T2 or FLAIR abnormalities apart from those consistent with radiation effect, and no new or increased enhancement;

c) patients should be on a corticosteroid dose that should not be greater than the dose at time of baseline scan, and should be stable or improved clinically

Stable Disease – SD (requires *all* of the following):

a) does not qualify for complete, partial, or minor response, or progression

b) stable area of non-enhancing abnormalities on T2 or FLAIR imaging;

c) no new lesions, no new T2 or FLAIR abnormalities apart from those consistent with radiation effect, and no new or increased enhancement; and

d) patients should be on a corticosteroid dose that should not be greater than the dose at time of baseline scan, and should be stable or improved clinically

Progressive Disease – PD (defined by *any* of the following):

a) development of new lesions or increase of enhancement (radiological evidence of malignant transformation);

b) a 25% increase of the T2 or FLAIR non-enhancing lesion on stable or increasing doses of corticosteroids compared with baseline scan or best response after initiation of therapy, not attributable to radiation effect or to comorbid events;

c) definite clinical deterioration not attributable to other causes apart from the tumor, or decrease in corticosteroid dose;

d) failure to return for evaluation because of death or deteriorating condition, unless caused by documented non-related disorder

8.2 Assessment of Response

Assessment of response will begin with the MRI performed just prior to *every odd-numbered* treatment cycle. If during any scheduled MRI, the subject has a Complete Response or Partial Response, the MRI should be repeated prior to the next cycle. All scans are to be compared to the smallest measurement scan to date. The subject will then return to the every odd-numbered cycle schedule. This is required to confirm the duration of response. Subjects will be classified as responders if they have a minimum duration of response for 4 weeks at any time after the first cycle of pamiparib (BGB-290). MRI scans of subjects showing tumor response will be centrally reviewed by a neuroradiologist who will independently assess tumor size and compute percent tumor regression. As a reminder, all assessments should be in compliance with the Imaging Core Manual.

ABTC # 1801

NCI # ABTC-1801

PI: [name]

8.3 Safety Assessments

Safety assessments will consist of monitoring and recording all adverse events and serious adverse events, the regular monitoring of hematology and blood chemistry, pregnancy testing (in women of childbearing potential), regular measurement of vital signs, and the performance of physical/neurological examinations; ECGs and other cardiac monitoring may be performed as necessary.

Monitoring Pregnancy

Pregnancy in itself is not regarded as an AE or SAE, however all reports of congenital abnormalities/birth defects, elective terminations for medical reasons and any serious complications of pregnancy (including spontaneous miscarriage, still birth and blighted ovum) should be reported as SAEs.

In the event of any occurrence of pregnancy in a patient or the female partner of a male patient, the site will complete and submit (via email of fax) the Pregnancy Notification Report (Appendix 5) within 24 hours of awareness. All pregnancy follow-up information should be sent to COV PV using the Pregnancy Follow-up Report (Appendix 6). Pregnancy Appendix 5 and 6 can be found at the ABTC Consortium Website www.abtconsortium.org

Monitoring of the patient should continue until conclusion of the pregnancy. The outcome of all pregnancies (live birth, spontaneous miscarriage, elective termination, or congenital abnormality/birth defects) must be followed up and documented, including patients who have discontinued the study, provided that the patient/partner provides consent. In addition, information about the pregnancy, the birth of the baby, and the health of the baby for up to 8 weeks after birth, even after study treatment has stopped, should be collected.

A female study participant who becomes pregnant must be withdrawn from the study; however, male study participants whose partner becomes pregnant can remain in the study.

Pregnancy cases will be followed-up every 3 months until final pregnancy outcome has been provided and a request for the outcome will also be issued within two weeks of the anticipated delivery date. Pregnancy reports will be tracked on a separate tab of the SAE tracker.

8.4 Quality Assurance

Neuropathology: The neuropathologic diagnosis of glioblastoma will be made at the respective institution. If any question arises regarding the accuracy of the neuropathologic diagnosis, slides (and pathological blocks, if necessary) will be reviewed by the central review pathologist. For protocols with "response" as an outcome, all patients with a

ABTC # 1801

NCI # ABTC-1801

PI: [name]

documented complete response or partial response may have representative pathology slides undergo central review.

Neuroradiology: MRI scans of patients showing tumor response as assessed locally will be centrally reviewed by the ABTC Imaging Core at the UCLA Brain Tumor Imaging Laboratory by board-certified neuroradiologists who will independently assess tumor size and assess radiographic response. Volumetric growth rates will be assessed by first performing volumetric (3D) contouring of the T2/FLAIR hyperintense lesion on historic (pre-treatment) and on-study scans by an imaging technologist. These segmentations will then be signed off by board-certified neuroradiologists prior to calculation of growth rates. Please refer to the Imaging Core Manual for further imaging requirements and submission information.

Adherence to protocol therapy: Screening/baseline source documentation will be submitted/uploaded into CTEP's iMedidata Rave system and will be reviewed by the ABTC Central Office. As a quality assurance measure for the treatment delivered on this protocol, primary patient records may be reviewed. The records to be examined will be selected retrospectively and at random; complete records must therefore be maintained on each patient treated on the protocol. These records should include primary documentation (e.g., laboratory report slips, X-ray reports, scan reports, pathology reports, physician notes, etc.), which confirm that:

- The patient met each eligibility criterion.
- Signed informed consent was obtained prior to treatment.
- Treatment was given according to protocol (dated notes about doses given; any reasons for any dose modifications).
- Toxicity was assessed according to protocol (laboratory report slips, etc.).
- Response was assessed according to protocol (MRI scan, lab reports, dated notes on measurements and clinical assessment, as appropriate).
- NCI Drug Accountability Records were maintained for this protocol.

NCI # ABTC-1801

PI: [name]

9.0 MONITORING OF PATIENTS

9.1 Tables of Required Observations

9.1.1 Phase I and Phase II (28-Day Cycles)

	Baseline	Days 1-28 of every cycle	Weekly During All Cycles	Pre-Odd Cycles (cycles 3+)	Pre-Even Cycles	Off Treatment	30 Days post-last dose
Pamiparib (BGB-290)		6					
Temozolomide		7					
AE Evaluation	1			5	5	8,10	11
Glucocorticoids Dose Evaluation	1			5		8	
MRI	1			5		8	
H&P/Neuro Exam	1			5	5	8	
KPS	1			5	5	8	
Vital Signs	1,2			2,5	2,5	2,8	
CBC, Diff, Platelets	1		9,13,15	5,9	5,9	8	
Serum Chemistry	1,3			3,5	3,5	3,8	
APTT or PTT	1						
Serum Pregnancy Test	14,4						
Urine Pregnancy Test				4,5	4,5	4	
Archived Tumor Tissue	12						

1- All baseline measurements must be done within minus 21 calendar days of treatment administration unless otherwise specified.

2– Including blood pressure, respiratory rate, heart rate, temperature, weight, height: height is required at baseline only; weight is required at pre-odd cycle evaluations only. Patients with dyspnea or asymptomatic desaturation (oxygen saturation <92%), will be further evaluated as clinically indicated: evaluation may include chest x-ray, arterial blood gas analysis, pulmonary function testing including diffusion capacity, co-oximetry, as well as evaluation for specific causes of hypoxia/dyspnea.

3- Including albumin, alkaline phosphatase, total bilirubin, calcium, creatinine, magnesium, phosphorus, potassium, SGOT, SGPT, sodium.

4– For women of child-bearing potential: monthly pregnancy tests through 6 months after completion of pamiparib (BGB-290) or temozolomide administration.

5- Within minus 5 calendar days of cycle start.

6- Pamiparib (BGB-290) is administered orally twice daily on Days 1-28 of each 28-day cycle (see Section 4.5.1). Patients are required to keep a medication diary.

7– TMZ is administered orally once daily according to the specified dose level of each 28-day cycle (see Section 4.5.2). Patients are required to keep a medication diary.

8- Evaluations done within +7 days of off treatment date unless indicated: do not repeat: if MRI within minus 14 days of off-treatment date (please refer to the Imaging Core Manual for further imaging requirements and submission information); if H&P/neuro, KPS, labs within minus 5 days of off-treatment date.

9– If ANC < 1500 or plts < 100,000, CBCs/differentials will be repeated twice a week until counts are recovered (ANC ≥1500 or plts ≥100,000) per protocol. If counts are recovered (ANC ≥1500 or plts ≥100,000) on day of scheduled drawing do not repeat until next protocol schedule day

10 - Adverse Events must be followed for at least 30 days from last dose of pamiparib (BGB-290).

11-Perform within +14 days of the 30-day post-last dose date.

12– Archived tumor tissue from a prior resection for glioma, preferably from the initial diagnosis, will be collected from all patients. See Section 9.5.1.

 $13\!-\!\pm 1~day$

14-Perform within minus 7 days of first dose

ABTC # 1801

NCI # ABTC-1801

PI: [name]

15- In subjects whose CBC, Diff, Platelets have been stable through the first 6 cycles, the frequency of hematologic testing can be reduced to a q2 weeks schedule (Day 15 of every cycle and Pre-cycle evaluation) starting in Cycle 7. CBC, Diff, Platelets will be considered "stable" if the following criteria are met: 1) No reports of ANC<1500/µl in ANY of the Cycles 1-6 weekly Labs and 2) No reports of Platelets<100,000/µl in ANY of the Cycles 1-6 weekly Labs and 2) No reports of Platelets<100,000/µl in ANY of the Cycles 1-6 weekly Labs. If at any point during treatment on the revised q2 weeks schedule the above mentioned ANC and Platelets criteria are not met, CBC, Diff, Platelets should be repeated twice a week until counts are recovered (ANC ≥1500 or Platelets ≥100,000). Once counts are recovered, the schedule of CBC, Diff, Platelets should go back to, and stay at, weekly monitoring (NOT q2 weeks).

IMPORTANT: The guidance below is subject to applicable local Institutional Policy on telemedicine. In the event that local Institutional Policy regarding telemedicine differs from this guidance, then please follow local Institutional Policy.

Telemedicine visits may be substituted for in person clinical trial visits or portions of clinical trial visits where determined to be appropriate and where determined by the investigator not to increase the participants risks. Prior to initiating telemedicine for study visits the study team will explain to the participant, what a telemedicine visit entails and confirm that the study participant is in agreement and able to proceed with this method. Telemedicine acknowledgement will be obtained in accordance with the Guidance for Use of Telemedicine in Research. In the event telemedicine is not deemed feasible, the study visit will proceed as an in-person visit. Telemedicine visits will be conducted using HIPAA compliant method approved by the Health System and within licensing restrictions.

Additionally, informed consent should be obtained in person, but if deemed necessary, via telemedicine.

	Baseline	Pre- Surgery	Day of Surgery	Post- Surgery	Post- Surgery Cycles	Weekly During All Cycles	Pre- Odd Cycles	Pre- Even Cycles	Off Treat- ment	30 Days post-last dose
Pamiparib (BGB-290)		6	6		6					
Temozolomide					7					
AE Evaluation	1		15	16			5	5	8,10	11
Glucocorticoids Dose Evaluation	1			16			5		8	
MRI	1			16			5		8	
H&P/Neuro Exam	1						5	5	8	
KPS	1						5	5	8	
Vital Signs	1,2						2,5	2,5	2,8	
CBC, Diff, Platelets	1					9,18,19	5,9	5,9	8	
Serum Chemistry	1,3						3,5	3,5	3,8	
APTT or PTT	1									
Serum Pregnancy Test	4,17									
Urine Pregnancy Test							4,5	4,5	4	
Archived Tumor Tissue	12									
Blood Samples for Pharmacokinetics	13		13							
Fresh Tumor Tissue			14							

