4.1.1 Dose Finding

Pamiparib (BGB-290) will be given at 60 mg BID at each dose/schedule; the dose of TMZ will be de-escalated/changing the treatment schedule, as shown in the table below if necessary:

Dose Level	Pamiparib (BGB-290)	Temozolomide Dose/Schedule
1 (starting dose)	60 mg BID	20 mg QD Days 1-28
-1	60 mg BID	20 mg QD Days 1-21
-2	60 mg BID	20 mg QD Days 1-14
-3	60 mg BID	20 mg QD Days 1-7

Phase I dose/schedule de-escalation

*Pamiparib (BGB-290) will be dose reduced only after discussion with Study Chair

The standard 3+3 design will be used for dose finding. Three patients will be enrolled per dose/schedule cohort. If no DLTs are observed in the first 3 patients at Dose Level 1, 3 additional patients will be enrolled at Dose Level 1 before pursuing Phase II of the protocol. If 1/3 of the patients develops a DLT during the first 4 weeks of treatment beginning from the first dose of pamiparib (BGB-290), Dose/Schedule Level 1 (or any subsequent dose/schedule level) will be expanded by 3 additional patients at the same dose/schedule level. The 3 additional patients must be followed for at least 4 weeks and toxicity evaluated before continuing.

Number of Patients with DLT at a Given Dose/Schedule	Decision Rule
0 out of 3	Enter 3 more patients at the same dose/schedule
1 out of 3	Enter 3 more patients at the same dose/schedule
2 out of 6	This is the maximum tolerated dose/schedule
2-3 out of 3, or \geq 3 out of 6	MTD exceeded, enter 3 patients at next lower dose/schedule

Dose-limiting toxicity (DLT) is defined in Section 5.1. No intra-patient dose escalation is allowed. Patients will be evaluable for the cohort if they have completed at least 80% of their expected dose of pamiparib (BGB-290) for the first treatment cycle (28 days). Patients who experience a DLT will be evaluable for the cohort if they have received at least one dose of pamiparib (BGB-290). The toxicity evaluation period is the first 4 weeks of treatment.

The target DLT rate is 33%. If the MTD is not reached among the pre-specified doses/schedules, the dose for the Phase II portion will be the highest dose/schedule studied for which the DLT rate is \leq 33% in 6 evaluable patients.

ABTC # 1801

NCI # ABTC-1801

PI: [name]

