4.5.2 Temozolomide Administration

Temozolomide will be administered orally on an outpatient basis once a day for the number of days indicated by the assigned dose level in 28-day cycles. On the days that pamiparib (BGB-290) is also taken, TMZ should be taken at the same time as the morning dose of pamiparib (BGB-290).

Because Temozolomide is intended for self-administration, if coming to the clinic presents a safety risk, it is permitted to ship the study drug and the appropriate medication diaries to the patient's residence before the scheduled cycle Day 1. The study drug should be shipped by a secure delivery method with package tracking and a delivery confirmation. The regulatory requirements for maintaining investigational product remain and should be addressed and documented.

Phase I Starting Dose: The starting dose of TMZ for the first cohort of patients in the Phase I portion will be a flat dose of 20 mg/day.

Phase II and Surgical Arm (post-surgical treatment cycles): TMZ will be administered at the dose established in the Phase I portion (*dose to be determined*).

Prior to each treatment cycle with temozolomide, a complete blood count (CBC) must be obtained (within -5 days prior to dosing). The start of all TMZ treatment cycles will be scheduled every 4 weeks (28 days, +3 days) after the first daily dose of temozolomide of the preceding treatment cycle.

If liver function tests (alkaline phosphatase, total bilirubin, SGOT, SGPT) are abnormal, the decision to initiate temozolomide treatment should carefully consider the benefits and
ABTC # 1801

NCI # ABTC-1801

PI: [name]

risks for the individual patient. For patients with significant liver function abnormalities, the benefits and risks of continuing treatment should be carefully considered.

Blood counts will be evaluated weekly. Within -5 days prior to first dose of each TMZ treatment cycle, the patient must have an ANC \geq 1500/ul and platelet count \geq 100,000/ul. On Day 1 of each cycle (within -5 days) all **non-hematological** toxicity grades 3 or 4 (except for alopecia, nausea and vomiting), related at least possibly to TMZ must have resolved (NCI Common Terminology Criteria for Adverse Events (CTCAE) grade \leq 1). If toxicity persists, treatment should be delayed by one week for up to 3 consecutive weeks. If after 3 weeks of delay all toxicity has still not resolved then any further treatment with temozolomide should be stopped. See Section 5.2.

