5.0 DOSE MODIFICATION FOR TOXICITY

5.1 Dose Limiting Toxicity (DLT)

A DLT is defined as a clinically significant adverse event or abnormal laboratory value assessed as unrelated to disease progression, intercurrent illness, or concomitant medications and meets any of the criteria below. Any DLT must be a toxicity considered at least possibly related to pamiparib (BGB-290) or TMZ.

ABTC # 1801

NCI # ABTC-1801

PI: [name]

Dose limiting toxicities (treatment related) are defined below. Dose limiting toxicities must have an attribution of possible, probable, or definite to pamiparib (BGB-290) or TMZ. For patients experiencing a DLT, pamiparib (BGB-290) and TMZ will be stopped. If the patient recovers (\leq grade 1 [or tolerable grade 2 for non-hematologic toxicity] or \leq baseline), refer to the Toxicity Management Table below for instruction on whether a dose reduction of TMZ or pamiparib (BGB-290) is required for subsequent doses, or whether pamiparib (BGB-290) and TMZ must be permanently discontinued. Skipped doses will not be made up. If there is any question or confusion concerning a DLT, the treating site should contact the ABTC Central Office to determine patient's DLT status. The ABTC Central Office, with the Study Chair, will make the final decision.

- → Hematological toxicities will be considered dose limiting if any of the following occur and complete blood counts and differentials were obtained according to the mandated schedule (CBC, differential, and platelets drawn twice a week until the ANC ≥ $1500/\mu$ L and platelets ≥100,000/µL): grade 3 or 4 lymphopenia will not be considered a DLT.
 - Grade 4 Neutrophil count decreased (ANC of $< 500/\mu$ L)
 - Grade 4 Platelet count decreased (Platelets $< 25,000/\mu$ L)
 - Grade 3 or 4 Febrile neutropenia
 - Any hematological toxicity that prevents administration of > 80% of the planned TMZ doses for the first cycle

Non-hematological toxicities will be considered dose limiting if any of the following occur:

- Grades 3-4 seizure or intracranial hemorrhage
 - All other grade 3 neurologic toxicity (other than seizure/intracranial hemorrhage) responding *within 3 days* to steroids, anticonvulsants, or electrolyte correction will not be considered dose limiting.
- Grades 3-4 severity with the following exceptions:
 - o except nausea, vomiting, and diarrhea without sufficient prophylaxis *lasting* ≤3 *days*;
 - except alopecia;
 - except grade 3 hyperglycemia;

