 - except grade 3 electrolyte disturbances that are asymptomatic and that respond to replacement therapy *within 3 days*;
 - A subject's first episode of deep venous thrombosis (DVT) or pulmonary embolism (PE) will not require dose modification (not a DLT).

ANY DLT (AS DEFINED ABOVE) CAUSING DELAY IN TREATMENT OF OVER 21 DAYS (OR OVER 14 DAYS FOR GRADE 3 HEPATIC TOXICITY) WITHOUT RECOVERY TO $A \leq$ GRADE 1 OR BASELINE STATUS WOULD RESULT IN TAKING THE PATIENT OFF TREATMENT.

ABTC # 1801

NCI # ABTC-1801

PI: [name]

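### Table 9.1.1 schedules one on-treatment serum chemistry in the 28-day DLT window, so transient liver or renal DLTs may be missed and the DLT rate biased downward by an amount the documents do not fix

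*Combined protocol and SAP*

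**What the plan says.** **Endpoint.** Phase I decides the schedule from DLTs in Cycle 1: "The toxicity evaluation period is the first 4 weeks of treatment" (section 4.1.1). Section 5.1 requires a DLT to be clinically significant and at least possibly related to study drug, and lets it be an abnormal laboratory value. Its non-hematological rule is "Grades 3-4 severity with the following exceptions". None of the exceptions covers transaminases, bilirubin or creatinine. One does cover electrolytes: "except grade 3 electrolyte disturbances that are asymptomatic and that respond to replacement therapy" within 3 days.

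**Chemistry schedule.** The row in Table 9.1.1 reads "Serum Chemistry 1,3 3,5 3,5 3,8". The entries fall under baseline, pre-odd cycles (from Cycle 3), pre-even cycles and off treatment. The Days 1-28 and weekly cells are blank. Footnote 3 gives the panel: "3- Including albumin, alkaline phosphatase, total bilirubin, calcium, creatinine, magnesium, phosphorus, potassium, SGOT, SGPT, sodium". Footnote 5 gives the pre-cycle window: "5- Within minus 5 calendar days of cycle start". Section 4.5.2 allows each cycle start to slip, being "scheduled every 4 weeks (28 days, +3 days) after the first daily dose of temozolomide" of the preceding cycle.

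**Comparison.** For hematology, "Blood counts will be evaluated weekly" (section 4.5.2), and Table 9.1.1 makes this twice weekly when counts are low. Adverse event evaluation, history and examination, and KPS have no entry between baseline and the pre-Cycle 2 visit. Section 8.3 asks for regular chemistry monitoring but gives no interval.

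**The concern.** A laboratory DLT without symptoms is counted only if someone draws blood while the value is abnormal. For counts, the plan matches sampling to the endpoint. For chemistry it offers one scheduled look near the end of the window, and possibly just beyond it. No scheduled mid-cycle contact exists that might prompt an extra test.

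A missed DLT moves the 3+3 decision in one direction only, toward accepting the schedule. The accepted schedule then goes to every Phase II patient and to the post-surgical cycles. Even where the late draw does find the abnormality, the patient may have been dosed through it: one that begins on day 8 and persists is first seen 16 to 20 days later (24 - 8 to 28 - 8).

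The Toxicity Management Table in section 5.2 also turns on whether bilirubin or creatinine recovers within 7 days and AST/ALT within 14 days, and the table of observations gives no chemistry interval fine enough to show this.

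**Working it through.** **1. Timing of the draw.** If Cycle 2 starts on day 29, the 5-day window gives days 24-28 (or day 29 before dosing). If Cycle 2 starts 3 days late, on day 32, the window is days 27-32 and the draw can fall after day 28.

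**2. The plan's own figure.** Section 4.1.1 accepts a level with 2 DLTs in 6 patients: 2/6 = 33.3%, which matches the stated 33% target.

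**3. Acceptance probability.** A level is accepted with 0 or 1 DLT in the first 3 patients and at most 2 in 6. With DLT probability p and q = 1 - p:

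A(p) = q³(1 - p³) + 3pq²(q³ + 3pq²)

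This gives 0.62 at p = 0.33, 0.48 at 0.40 and 0.30 at 0.50.

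**4. Detection.** Onset and duration are not in the documents. Assume onset uniform over days 1-28.
- One draw on a day t in 24-28, event lasting d days (d up to 24): d of the 28 onset days lead to detection, so the probability is d/28.
- Persistent event: detected if onset is on or before t, so t/28, averaging 26/28 over t = 24 to 28.
- Weekly draws on days 8, 15, 22 and 28: count the onset days covered by at least one draw.

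| Duration | Single draw | Weekly draws |
|---|---|---|
| 3 days | 3/28 = 0.11 | 12/28 = 0.43 |
| 7 days | 7/28 = 0.25 | 27/28 = 0.96 |
| 14 days | 14/28 = 0.50 | 28/28 = 1.00 |
| Persistent | 26/28 = 0.93 | 28/28 = 1.00 |

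**5. Effect on the 3+3 decision.** Assume a 30% hematologic DLT rate, an independent chemistry DLT rate c, and detection probability D. The observed rate is 0.30 + 0.70 × c × D. Neither rate is in the documents; c is varied to show the range.

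| c | All seen: p, A(p) | Single draw, 7-day events (D = 0.25) | Single draw, persistent (D = 0.93) |
|---|---|---|---|
| 5% | 0.335, 0.61 | 0.309, 0.66 | 0.333, 0.62 |
| 15% | 0.405, 0.47 | 0.326, 0.63 | 0.398, 0.49 |
| 20% | 0.440, 0.40 | 0.335, 0.61 | 0.430, 0.42 |

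Worked line for c = 20%, all seen: q = 0.56, q³ = 0.1756, 3pq² = 0.4140, so A = 0.1756 × 0.9148 + 0.4140 × 0.5896 = 0.405.

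**6. Cross-check with another parameterization.** Fix the true DLT rate at 50% and let a share s of DLTs be visible only in chemistry, each lasting 7 days. The observed rate is 0.50(1 - s) + 0.50 × s × 0.25. For s = 10%, 25% and 50% this is 0.463, 0.406 and 0.313, and acceptance is 0.36, 0.47 and 0.66, against 0.30 with full detection.

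**The case against.** The best counter-argument concerns duration. The large effect needs a grade 3-4 abnormality that resolves by itself within about a week while pamiparib, and TMZ at the starting level, are given every day. The 7- and 14-day limits in section 5.2 are recovery times after both drugs are held, so they do not support such a short duration on treatment. If abnormalities persist under dosing, the single draw finds 0.93 of them and the acceptance gap is about 2 points. This stands, and it is why no single figure can be given.

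Onset may also be late. Section 9.2.1.2 says temozolomide liver toxicity can appear several weeks into treatment. With onset on days 15-28, the single draw finds 7/14 = 0.50 of 7-day events. The toxicity that the documents report for the combination is chiefly hematologic: section 2.2 describes neutropenia and thrombocytopenia above the MTD at TMZ 40 mg. A small chemistry share is therefore plausible. Both points limit the size but leave the direction unchanged.

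A reader might infer that chemistry DLTs cannot be seen at all. The documents do not support that. Section 9.1 lists required observations and does not bar extra tests, section 9.2.2 asks for close monitoring, and patients going off treatment have chemistry drawn. A reader might also make much of electrolytes and glucose. Asymptomatic grade 3 electrolyte changes that respond within 3 days are excepted, and so is grade 3 hyperglycemia, which makes both minor.

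Finally, repeat testing while drug is held is already implied, since dosing resumes only on recovery. What is missing there is a stated interval.

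**Conclusion.** The point holds as an ascertainment gap. One scheduled chemistry draw, late in or just after the DLT window, is a thin basis for an endpoint that counts liver and renal laboratory values over 28 days. The resulting error in the DLT rate can only be downward.

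Its size is not determined by the documents. For 7-day events, acceptance rises by 16 to 21 points if chemistry DLTs occur in 15-20% of patients and by about 5 points if they occur in 5%. For persistent events at the 15-20% rate it rises by about 2 points, and the main cost is late discovery. All of these figures rest on uniform onset, an assumed 30% hematologic rate and independence of the two kinds of DLT.

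It would be tempting to conclude that a too-toxic schedule will probably be accepted, at 0.61-0.63. That is the upper part of the range under assumptions without a source in the documents, and should not be read as an estimate.

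**What to change.** In Table 9.1.1, add the footnote 3 chemistry panel to the existing weekly CBC draw in Cycle 1 for Phase I patients. The cost is a schedule-table amendment and about three extra panels per patient on blood already being drawn: 18 to 54 panels for the planned 6-18 patients, or 72 if all four levels fill with 6 patients each (24 × 3). Detection of a 7-day event rises from 0.25 to 0.96. For 3-day events it reaches only 0.43, so weekly chemistry does not remove the gap completely. No dose, DLT definition or stopping rule changes.

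Separately, the sponsor should reconcile the 7- and 14-day hepatic and creatinine limits in the Toxicity Management Table with the chemistry schedule, so that it is clear how those limits are to be assessed.
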